10.2 Visit 2 (Day 7-10 ±1 days)

1. Provide CRISS Self-Report to subject for completion.
2. Provide EQ-5D-5L to subject for completion.
3. Measure and record weight.
4. Perform and record spirometry.
5. Collect subject health care resource use information.
6. Record any respiratory microbiology results since Visit 1.
7. If Chemistry tests for BUN, creatinine and serum glucose have been collected for clinical care, obtain results and record.
8. Record changes to concomitant medications.
9. Perform abbreviated physical examination.
10. Re-confirm eligibility.
11. Enter required data into EDC for randomization (refer to CRF Completion Guidelines, includes CRISS and spirometry).
12. Randomize subject to treatment duration.
13. If able to expectorate, collect expectorated sputum for microbiome.
14. Collect blood and test for CRP at site.
15. Collect blood and freeze serum for banking.
16. Record any adverse events.
17. Schedule subject for Visit 3 dependent on treatment arm and to occur 2 weeks after scheduled completion of IV treatment.

10.3 Visit 3 (Follow-up 2 weeks after scheduled completion of IV treatment /Day 24 – 35 +/-2 days)

1. Provide CFRSD Self-Report to subject for completion.
2. Provide EQ-5D-5L to subject for completion.
3. Collect subject health care resource use information.
4. Record any respiratory microbiology results since Visit 1.
5. If Chemistry tests for BUN, creatinine and serum glucose have been collected for clinical care, obtain results and record.
6. Record any adverse events.

7. Record changes to concomitant medications.
8. Perform abbreviated physical examination.
9. Measure and record weight.
10. Perform and record spirometry.
11. If able to expectorate, collect expectorated sputum for microbiome.
12. Collect blood and test for CRP at site.
13. Collect blood and freeze serum for banking.

11 ADVERSE EXPERIENCE REPORTING AND DOCUMENTATION

11.1 Adverse Events

An adverse event (AE) is any untoward medical occurrence in a subject that is participating in this clinical investigation that is related to study participation (treatment arm assignment), study procedures, or any other significant AE as determined by the investigator.

AEs are defined as new or worsening of signs or symptoms, including clinically significant abnormal clinical laboratory values, that occur after randomization (Visit 2) until Visit 3.

An unexpected AE is one of a type not identified in nature, severity, or frequency or of greater severity or frequency than expected.

The Investigator will probe, via discussion with the subject, for the occurrence of AEs and record the information in the site's source documents. AEs will be recorded in the subject CRF.

AE Severity

The National Cancer Institute's Common Terminology Criteria for Adverse Events (CTCAE) Version 4.0, as modified for cystic fibrosis, should be used to assess and grade AE severity, including laboratory abnormalities judged to be clinically significant. The modified criteria can be found in the Study Reference Binder. If the experience is not covered in the modified criteria, the guidelines shown in Table 1 below should be used to grade severity. It should be pointed out that the term "severe" is a measure of intensity and that a severe AE is not necessarily serious.

Table 1. AE Severity Grading

Severity (Toxicity Grade)	Description
Mild (1)	Mild; asymptomatic or mild symptoms; clinical or diagnostic observations only; intervention not indicated
Moderate (2)	Moderate; minimal, local or noninvasive intervention indicated; limiting age-appropriate Instrumental activities of daily living (e.g., preparing meals, using the telephone, managing money)
Severe (3)	Severe or medically significant but not immediately life-threatening; hospitalization or prolongation of hospitalization indicated; disabling; limiting self care activities of daily living (e.g., bathing, dressing, feeding self, using toilet, taking medications)

Life-threatening (4)	Life-threatening consequences; urgent intervention indicated
Death (5)	Death related to AE

AE Relationship to Treatment Arm Assignment

The relationship of an AE to the treatment arm assignment should be assessed using the following the guidelines in Table 2.

Table 2. AE Relationship to Treatment Arm Assignment

Relationship to Treatment	Comment
Definitely	An event that follows a reasonable temporal sequence from the clinical trial treatment arm assignment; that follows a known or expected response pattern to treatment arm assignment; and that is not explained by any other reasonable hypothesis.
Probably	An event that follows a reasonable temporal sequence from the clinical trial treatment arm assignment; that follows a known or expected response pattern to treatment arm assignment; and that is not explained by any other reasonable hypothesis; and that is unlikely to be explained by the known characteristics of the subject's clinical state or by other interventions.
Possibly	An event that follows a reasonable temporal sequence from the clinical trial treatment arm assignment; that follows a known or expected response pattern to treatment arm assignment; but that could readily have been produced by a number of other factors.
Unrelated	An event that can be determined with certainty to have no relationship to the treatment arm assignment.

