2.3 Adverse Events

All reported SAEs and AEs are coded using MedDRA and grouped by body system. (S)AEs are tabulated by treatment durations within ERR and NERR groups using standard coding terms sorted by body system. The incidence of AEs (including emergent abnormal lab values collected for clinical care) in each treatment duration arm is tabulated by seriousness, severity, and relationship to arm. If an AE is reported more than once during the study period for a given subject, the greatest severity and the worst-case relationship is presented in tables. The number of (S)AEs is summarized by treatment duration arms within ERR and NERR groups as follows: (i) The proportion of subjects with at least one (S)AE, (ii) The average number of (S)AEs per patient, and (iii) The rate of (S)AEs per patient week of follow-up. Histograms showing the frequency of the number of (S)AEs in each treatment duration arm are included. Rates of (S)AEs by System Organ Class (SOC) are presented by treatment duration arm. Poisson regression modeling is used to derive rate ratios and 95% confidence intervals for each SOC. The rate ratios is compared using a two-sided 0.05 level test for Poisson count data.

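### The causality table gives no rule for separating Definitely from Probably, so the split between those two grades in the adverse event tables cannot be interpreted

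*Protocol*

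**What the plan says.** Protocol 11.1 makes Table 2 the operative guide to causality: "The relationship of an AE to the treatment arm assignment should be assessed using the following the guidelines in Table 2". The table has four grades.

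- Definitely has three conditions. The one on timing is "An event that follows a reasonable temporal sequence from the clinical trial treatment arm assignment". The one on pattern is "that follows a known or expected response pattern to treatment arm assignment". The one on alternative explanations is "and that is not explained by any other reasonable hypothesis".
- Probably repeats all three of these word for word. It then adds a fourth, which opens "and that is unlikely to be explained by the known characteristics of the" and turns to the patient's clinical state and other interventions.
- Possibly keeps only the first two, on timing and pattern, with the qualification "but that could readily have been produced by a number of other factors".
- Unrelated is for events that can be said with certainty to have no relationship.

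Protocol 15.4 and SAP 2.3 both tabulate adverse events in each duration arm by seriousness, severity and relationship to arm. Where a patient has the same event more than once, "the greatest severity and the worst-case relationship is presented in tables". The SAP neither redefines the four grades nor says that any of them will be pooled.

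**The concern.** A graded causality scale works only if each step up asks for more evidence. Here the step from Probably to Definitely asks for no more, and on a literal reading asks for less. A site with an event that has no other reasonable explanation has nothing in the table to tell it which of the two labels to use.

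The planned tables report the two grades separately. The worst-case rule for repeated events also assumes that one of them ranks above the other on substance. If sites resolve the ambiguity differently, the split reflects site habit and not strength of evidence.

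Clear grades matter here because safety is part of the primary objective in both response groups (Protocol 3.1). Treatment is also open-label, so investigators grade relationship to an arm they know, and neither document describes a blinded causality assessment.

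**Working it through.** No arithmetic in the plan bears on this point, so the check compares the clauses of Table 2.

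**Inputs.** All come from Protocol 11.1, Table 2.

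| Label | Condition | Definitely | Probably | Possibly |
|---|---|---|---|---|
| A | plausible timing | yes | yes | yes |
| B | recognised pattern | yes | yes | yes |
| C | no other reasonable hypothesis | yes | yes | – |
| D | unlikely to be due to clinical state or other interventions | – | yes | – |
| E | other factors could readily have caused it | – | – | yes |

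**Step 1: literal reading.** Conditions A to D can each be true or false, which gives 2 × 2 × 2 × 2 = 16 combinations.
- Definitely (A, B and C) is met by 2 of them: A, B and C true, with D true or false.
- Probably (A, B, C and D) is met by 1.
- That 1 is among the 2 that meet Definitely, so the number meeting Probably alone is 1 − 1 = 0. The weaker label has the narrower definition.

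**Step 2: reading D as redundant.** Clinical state and other interventions are themselves other hypotheses, so C may already imply D. The combination with C true and D false then cannot occur. Definitely falls to 2 − 1 = 1 combination, the same one as Probably, and the two grades are identical.

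**Step 3: what remains readable.** On both readings Definitely and Probably require C. Possibly does not, and its condition E points the other way. Definitely and Probably added together can therefore be read against Possibly and Unrelated.

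**Step 4: deleting C from Probably only.** Probably becomes A, B and D, which 2 of the 16 combinations meet (C true or false). One of these also meets Definitely, so 2 − 1 = 1 combination now belongs to Probably alone. If C implies D, Definitely is 1 combination nested inside Probably's 2, so the higher grade is the stricter one. Possibly stays apart because E is at odds with D.

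**Step 5: a tempting alternative.** Suppose D were moved up to Definitely and C were also deleted from Probably. Probably would then be A and B only. Possibly is A, B and E, so every Possibly event would also meet Probably. That is the same fault one level down.

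**The case against.** The strongest reply is that this is a drafting slip with little practical effect. Table 2 is offered as guidance, the labels have an evident order, and an experienced investigator will rank Definitely above Probably whatever the clauses say. Instructions for completing the case report form, which we have not seen, may clarify the matter. Much of this is fair, and it limits the size of the point. It does not supply a rule: the order of the labels says which is higher, not which events belong in each.

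Four stronger readings are tempting, and the documents do not support them.

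- A reader might infer that the scale is simply inverted. That holds only on the literal reading; if the added clause is redundant, the grades are indistinguishable and not reversed.
- A reader might infer that Definitely will be inflated. An event that meets both definitions could be put in either, and a site could prefer Probably as the fuller description. The text shows ambiguity without a direction.
- A reader might infer that the SAP takes one worst-case relationship per patient over all events. The rule covers only repeats of an event within a patient. It is touched here only when those repeats are graded differently across the top two grades.
- A reader might infer that the lower end is equally faulty, because Unrelated demands certainty and some events may then fit no grade. That is a separate question. The demand for certainty may be a deliberate conservative default, and nothing in the documents shows otherwise.

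**Conclusion.** The point holds in a narrow form. As written, Table 2 does not distinguish Definitely from Probably, and nothing in the SAP repairs this. The split between the two grades cannot be interpreted, and neither can the worst-case relationship of a repeated event that received both.

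The number of events concerned cannot be estimated, because the documents give no expected frequencies by grade and do not show how sites grade in practice. Event counts, rates, severity and seriousness are unaffected, as are the Poisson rate ratios by System Organ Class and both FEV₁ analyses. Serious events are documented whether or not they are judged related (Protocol 11.2.1). This is a minor correction to safety reporting and does not threaten the trial's conclusions.

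The verdict assumes that Table 2 as supplied is complete, which its sentences suggest, and that no site instruction outside these documents defines the grades differently.

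**What to change.** In Protocol 11.1, Table 2, delete the clause on other reasonable hypotheses from Probably only, and keep the clause on clinical state and other interventions there. Leave Definitely, Possibly and Unrelated as they are. Rewording the last two would move the boundary between related and unrelated events without helping with this problem.

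In the SAP, section 2.3, prespecify a pooled Definitely plus Probably row, shown against Possibly and Unrelated, so that events graded under the present wording remain usable.

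The cost is one clause in a protocol amendment, the same change in any site material that repeats the table, and one row in the SAP tables. Protocol 15.3 has the SAP finalised before data lock, and the pooled row needs no new data.

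The downside is that the Definitely/Probably split will not be comparable before and after the rewording. The pooled row removes the need to rely on that split. One small residue remains: an event that meets D but not C falls outside both top grades today and would enter Probably afterwards. If most events have already been graded, adding the pooled row without changing the table avoids this.

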11.2 Serious Adverse Experiences (SAE)

An SAE is defined as any AE occurring that results in any of the following outcomes:

- death
- a life-threatening adverse experience
- inpatient hospitalization (excluding the initial enrollment hospitalization) or hospitalizations that occur after the initial enrollment and start of IV antibiotic treatment at home will be reported
- prolongation of existing hospitalization beyond the planned duration as indicated by randomization
- a persistent or significant disability/incapacity
- a congenital anomaly/birth defect

Other important medical events may also be considered an SAE when, based on appropriate medical judgment, they jeopardize the subject or require intervention to prevent one of the outcomes listed.

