STUDY DESIGN	This randomized, controlled, open-label study is designed to evaluate the efficacy and safety of differing durations of IV treatment, given in the hospital or at home for a pulmonary exacerbation in adult patients with CF. The study will assess the non-inferiority of 10 days versus 14 days treatment duration among ERR subjects and the superiority of 21 days versus 14 days treatment duration among the subjects who do not meet the definition of ERR (non-ERR; NERR) Subjects will undergo pulmonary function testing (spirometry) and complete a respiratory symptom score [Chronic Respiratory Infection Symptom Score (CRISS)] at initiation of IV treatment (Baseline/ Visit 1) and at Day 7-10 (Visit 2). At Visit 2, subjects will be allocated to groups ERR or NERR based on their initial clinical response as determined by the change in forced expiratory volume in 1 second (FEV ₁ ; percent of predicted) and CRISS from Baseline and then randomized to an IV treatment duration (nested within group). ERR subjects [$\geq 8\%$ predicted improvement in FEV ₁ from Baseline (Visit 1) to Visit 2 and CRISS reduction of ≥ 11 points from Baseline (Visit 1) to Visit 2] will be randomized 1:1 to either 10 days or 14 days total IV antibiotic treatment duration. Remaining (NERR)

	
subjects will be randomized 1:1 to receive either 14 or 21 days total IV antibiotic treatment duration. All subjects will be evaluated again at Visit 3, 14 days following scheduled completion of IV antibiotic treatment.

DURATION OF SUBJECT PARTICIPATION AND DURATION OF STUDY
	
Dependent on the treatment arm, subjects will be on study from 24 to 35 days:
 
 ▪ Treatment prior to randomization: 7 – 10 days ▪ Treatment post-randomization: 
 ○ ERR-10 subjects: 0 to 3 days = 10 days (± 1 day) total IV treatment ○ ERR-14 subjects: 4 to 7 days = 14 days (± 1 day) total IV treatment ○ NERR-14 subjects : 4 to 7 days = 14 days (± 1 day) total IV treatment ○ NERR-21 subjects: 11 to 14 days = 21 days (± 3 days) total IV treatment ▪ Follow-up: 14 days after end of scheduled IV antibiotic treatment (± 2 days) 
The total duration of the study is expected to be approximately 42 months: 41 months for subject recruitment and 1 month for final subject follow-up.

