6.3 Exclusion Criteria

1. Previous randomization in this study
2. Treatment with IV antibiotics in the 6 weeks prior to Visit 1
3. Admission to the intensive care unit for current pulmonary exacerbation in the two weeks prior to Visit 2, unless admission was due to a desensitization protocol
4. Pneumothorax in the two weeks prior to Visit 2
5. Primary diagnosis for current hospitalization is unrelated to worsening lower respiratory symptoms (e.g., pulmonary clean out, DIOS, sinusitis)
6. Massive hemoptysis defined as > 250 cc in a 24 hour period or 100 cc/day over 4 consecutive days occurring in the two weeks prior to Visit 2
7. Current pulmonary exacerbation thought to be due to allergic bronchopulmonary aspergillosis (ABPA)
8. At Visit 1, receiving ongoing treatment with a duration of more than 2 weeks with prednisone equivalent to >10mg/day
9. History of solid organ transplantation
10. Receiving antimicrobial therapy to treat non-tuberculous mycobacterium (e.g., *M. abscessus*, *M. avium* complex) in the two weeks prior to Visit 2

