8.3 Treatment Location

The location of treatment (i.e., home vs. hospital) is at the discretion of the treating clinician. The patient may be treated entirely at home, entirely in the hospital, or any portion of treatment in the hospital with completion at home.

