9.1.11 Adverse Events

Information regarding occurrence of AEs will be captured throughout each subject's study participation, starting at randomization and ending once the subject has terminated from the study. Duration (start and end dates), grade, seriousness, outcome, treatment, and relation to study treatment arm will be recorded on the CRF.

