11.2.1 Serious Adverse Experience Reporting

Study sites will document all SAEs that occur (whether or not related to treatment arm assignment) on an SAE Report Form. The collection period for all SAEs will begin after informed consent is obtained and end after procedures for the final study visit have been completed.

All SAE Report Forms will be reviewed by the site investigator and sent to the TDNCC within one business day of the site learning of the event. Sites will send the SAE report by either:

- Email (scanned copy) to: [contact]
- TDNCC SAE [contact]

The site will notify the TDNCC of additional information or follow-up to an initial SAE Report as soon as relevant information is available. The TDNCC Medical Monitor may request additional information related to the SAE. Follow-up information is reported on an SAE Report Form.

In accordance with the standard operating procedures and policies of the local Institutional Review Board/Independent Ethics Committee (IRB/IEC), the site investigator will report SAEs to the IRB/IEC.

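### Minor, cheap improvement: SAP 2.3 sets no SAE onset limit or patient-time start for the by-arm comparison, and should flag SAEs that are serious only because a stay outlasted the randomised duration

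*Protocol*

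**What the plan says.** **Seriousness.** Protocol 11.2 treats an SAE as a subset of adverse events. One qualifying outcome is "prolongation of existing hospitalization beyond the planned duration as indicated by randomization". The Synopsis gives planned durations of 10 and 14 days (each ±1) in ERR, 14 days (±1) in NERR-14, and "NERR-21 subjects: 11 to 14 days = 21 days (± 3 days) total IV treatment". Section 11.2 does not say whether these tolerances count. Section 8.3 allows "any portion of treatment in the hospital with completion at home", so length of stay and length of IV course can differ.

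**Onset.** Protocol 11.1 restricts adverse events to those "that occur after randomization (Visit 2) until Visit 3", and 9.1.11 agrees ("starting at randomization and ending once the subject has terminated from the study"). Section 11.2.1 differs: "The collection period for all SAEs will begin after informed consent is obtained".

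**Analysis.** SAP 2.3 tabulates all reported SAEs by arm and gives rates per patient week (Protocol 15.4: per patient month). It tests rate ratios by system organ class. It gives no onset limit, no start of patient time and no breakdown by seriousness criterion. SAP 1.2 sends by-arm SAE tables to the DSMB twice a year.

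**The concern.** Safety relative to 14 days is part of the primary objective in both groups (Protocol 3.1). Protocol 15.7 names the potential toxicity of 21 days as something the FEV₁ benefit must justify. The by-arm SAE tables should therefore compare like with like, and two features work against that.

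- **Onset.** Read literally, SAP 2.3 brings SAEs from the 7-10 days before randomisation into a comparison of arms that did not yet exist. The patient-time denominator is undefined.
- **Prolongation.** The threshold for a prolonged stay is itself the randomised factor. An event that keeps a subject in hospital to day 18 can be serious in NERR-14 and not in NERR-21. A stay to day 13 can be serious in ERR-10 and not in ERR-14.

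**Working it through.** **The plan's own figures.** There is no SAE rate or safety power to reproduce. The time on study does reproduce: 10 + 14 = 24 days at the shortest and 21 + 14 = 35 at the longest, as stated.

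**Post-randomisation time**, with Visit 2 on day V = 7 or 10:

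| Arm | Formula | V = 7 | V = 10 |
|---|---|---|---|
| ERR-10 | 24 − V | 17 | 14 |
| ERR-14 | 28 − V | 21 | 18 |
| NERR-14 | 28 − V | 21 | 18 |
| NERR-21 | 35 − V | 28 | 25 |

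The longer-to-shorter ratio k is 1.33-1.39 in NERR and 1.24-1.29 in ERR.

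**Onset.** Let f be the pre-randomisation SAE rate divided by the later NERR-14 rate (assumed), with all SAEs counted and a true NERR-21/NERR-14 rate ratio of 2.0.

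- Patient time from randomisation: [(fV + 2(35−V))/(35−V)] / [(fV + 28−V)/(28−V)].
- Patient time from day 1: [(fV + 2(35−V))/35] / [(fV + 28−V)/28].

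| f | From randomisation (V = 7 / 10) | From day 1 (V = 7 / 10) |
|---|---|---|
| 0.10 | 1.96 / 1.93 | 2.09 / 2.15 |
| 0.25 | 1.90 / 1.84 | 2.03 / 2.05 |
| 0.50 | 1.82 / 1.72 | 1.94 / 1.91 |

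For f = 0.10-0.25 the shift is at most about 8% (1.84/2 = 0.92). The early events balance between arms on average. The rise above 2.0 when time starts at day 1 comes from the denominator: the longer arm has a smaller share of low-rate time. With a true ratio of 1.0 (replace the 2 by 1) and the same f, the results are 0.97-0.99 from randomisation and 1.05-1.09 from day 1. So the start of patient time needs stating as well as the onset limit.

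**Prolongation zone.** On nominal durations it is days 15-21 in NERR and 11-14 in ERR. If the Synopsis tolerances count, it is days 16-24 in NERR (14+1 to 21+3) and 12-15 in ERR (10+1 to 14+1).

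**Prolongation, size in NERR.** Assume equal daily risk of other SAEs in both arms, with:

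- o = other-SAE risk in NERR-14;
- x = prolongation-only SAE risk in NERR-14 (2%);
- y = prolongation-only SAE risk in NERR-21, that is, stays beyond day 21.

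Rate ratio = (k·o + y) / (k·(o + x)). Raw proportion ratio = (k·o + y) / (o + x). The true rate ratio is 1.0.

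| o | Rate, y = 0 | Rate, y = 2% | Raw, y = 0 | Raw, y = 2% |
|---|---|---|---|---|
| 3% | 0.60 | 0.89-0.90 | 0.80-0.83 | 1.20-1.23 |
| 5% | 0.71 | 0.92-0.93 | 0.95-0.99 | 1.24-1.28 |
| 10% | 0.83 | 0.95-0.96 | 1.11-1.16 | 1.28-1.32 |

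The rate ratio is below 1 while k·o + y < k·o + k·x, that is, while y < 1.33-1.39 times x.

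**Chance of a false signal.** At y = 0 and 285 per arm, the expected NERR-21 v NERR-14 counts are 11-12 v 14, 19-20 v 20 and 38-40 v 34. The exact conditional Poisson p is 0.23-0.48. The chance of p < 0.05 in an overall rate test is 11-23%, against about 4% with x = 0. At y = 2% it is about 5%. SAP 2.3 plans no overall SAE test, and its tests by system organ class rest on smaller counts.

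**The case against.** **The stronger reading.** A reader might infer that the definition systematically makes NERR-21 look safer, turning a true ratio of 1.0 into 0.60-0.83. The documents do not support that. Those figures give NERR-21 no stay prolonged beyond day 21. For a subject treated in hospital to the end of the course, a three-day delay ends on day 17 in NERR-14 and day 24 in NERR-21, and on nominal durations both meet the criterion. The asymmetry is confined to stays whose end day does not depend on arm. This objection stands, and it removes the y = 0 ratios as a headline.

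**Partial safeguards exist.** Protocol Table 1 grades an event needing prolonged hospitalisation as severe (Grade 3) without reference to the randomised duration, though only for events outside the modified CTCAE. SAP 2.3 tabulates severity by arm. The important-medical-event clause can make such an event serious in either arm. These points stand as mitigation. The narratives in SAP Appendix A cover SAEs only, so a stay that never met the definition has none.

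**The onset conflict is largely editorial.** Sections 9.1.11, 11.1 and 11.2 already point to randomisation. Section 6.3 excludes "Admission to the intensive care unit for current pulmonary exacerbation in the two weeks prior to Visit 2" (desensitisation excepted), as well as pneumothorax and massive hemoptysis in that window, and Visit 2 includes the step "Re-confirm eligibility". This supports a modest effect but does not tell the programmer which events to count.

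**The remedy is imperfect.** Removing prolongation-only events also removes NERR-21 stays beyond day 21 and leaves the new-hospitalisation criterion asymmetric. A NERR-14 subject discharged on day 14 and readmitted has an SAE; a NERR-21 inpatient with the same event, resolved by day 21, may not. This stands, so the second result can only be a supplement.

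**Conclusion.** The point holds as a minor, cheap improvement to the safety analysis. It does not touch the FEV₁ analysis.

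- **Onset.** The SAE start points conflict, and SAP 2.3 does not settle which applies. Early SAEs dilute the comparison rather than bias it, apart from a small denominator effect if patient time starts at day 1. The shift is within about 8% of a true NERR ratio of 2.0 for f = 0.10-0.25, and up to 14% at f = 0.50 (1.72/2 = 0.86).
- **Prolongation.** Seriousness can depend on arm for stays ending between the two planned durations. Rates lean towards NERR-21 only while its prolonged-stay risk is below about 1.33-1.39 times that of NERR-14. With 2% in each arm a true 1.0 appears as 0.89-0.96. In ERR the zone counts against ERR-10, the arm under test.

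The net direction in raw counts cannot be determined, and a false significant result is not the likely outcome. All of this rests on assumed SAE risks, equal daily risk and nominal visit days. The share of subjects still in hospital is also unknown.

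**What to change.** In SAP 2.3, with the SAE definition and SAE reporting unchanged:

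1. **Onset and patient time.** Limit by-arm SAE comparisons to onset after randomisation, start patient time at randomisation, and list earlier SAEs separately. Add a line reconciling Protocol 9.1.11, 11.1 and 11.2 with 11.2.1, and settle on one rate unit.
2. **Prolongation flag.** Flag SAEs whose only seriousness criterion is prolonged hospitalisation. List them by arm with the day the stay ended. Show the SAE rate with and without them as a descriptive supplement to the full table, read beside the planned severity table for Grade 3 or higher events.

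**Cost.** One rule, one flag, one listing and one extra table, with no new visits or procedures. This assumes that the SAE form, which the documents do not show, records the seriousness criterion.

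**Limits to state with the table.** Without the flagged events it omits genuine prolongations, including NERR-21 stays beyond day 21, so it can itself favour NERR-21. It does not correct the new-hospitalisation asymmetry or recover events never reported as serious.
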